# 2. SYNOPSIS

2.1	Protocol Title: Active Clearance Technology ® Improves Post Operative Atrial Fibrillation- The ACT POAF Trial
2.2	Protocol Number: MP-33-2015-1901
2.3	Sponsor: ClearFlow, Inc. has provided partial support for this trial
2.4	
 
Objectives:
 
1. To assess the effectiveness of the PleuraFlow® Active Clearance Technology® (ACT) in reducing the rate of postoperative atrial fibrillation (POAF) among post cardiac surgery patients
 
2. To evaluate the impact of ACT on retained blood syndrome
 

	(RBS) and other complications after cardiac surgery.

This is a prospective, randomized, single blinded two-arms, single-center Post Market Clinical Follow-Up (PMCF) Study. The test arm consists of consecutively enrolled cardiac surgery patients receiving $\leq$ two (2) PleuraFlow ® chest tubes with Active Clearance Technology ® and $\leq$ two (2) other commercially available chest tubes. The 1 control arms consist of consecutively enrolled cardiac surgery patients receiving $\leq$ four (4) commercially available standard chest tubes. In all arms, one (1) chest tube must be placed in the anterior mediastinum. The other chest tube(s) may be placed at the discretion of the operator. Chest tubes with internal diameter 28 FR to 32 FR shall be used.
Study Population:
-Up to 508 evaluable post-cardiac surgery female and male subjects, 18 years of age and older will be consecutively enrolled in the study.
- Subjects are required to meet all inclusion criteria and none of the exclusion criteria to be included in this PMCF study. Subjects must be informed about this study and a written and signed informed consent must be obtained from the subject prior to cardiac surgery.
Number of Subjects/sites:
Up to 508 evaluable subjects enrolled at the Montreal Heart Institute and Sacré-Coeur of Montreal Hospital
Up to 508 evaluable subjects enrolled at the Montreal Heart
Up to 508 evaluable subjects enrolled at the Montreal Heart Institute and Sacré-Coeur of Montreal Hospital Gender/Age:
Up to 508 evaluable subjects enrolled at the Montreal Heart Institute and Sacré-Coeur of Montreal Hospital Gender/Age: Females and males, 18 years of age and older.
Up to 508 evaluable subjects enrolled at the Montreal Heart Institute and Sacré-Coeur of Montreal Hospital Gender/Age: Females and males, 18 years of age and older. Inclusion Criteria:
Up to 508 evaluable subjects enrolled at the Montreal Heart Institute and Sacré-Coeur of Montreal Hospital Gender/Age: Females and males, 18 years of age and older. Inclusion Criteria: Subjects will be required to meet all Inclusion Criteria: 1. Admission for CABG, valve replacement or valve repair

 
Up to 508 evaluable subjects enrolled at the Montreal Heart Institute and Sacré-Coeur of Montreal Hospital
 
Gender/Age: Females and males, 18 years of age and older.
 
Inclusion Criteria: Subjects will be required to meet all Inclusion Criteria:
 
Admission for CABG, valve replacement or valve repair surgery, or a combination of these surgeries;
 
Surgical procedure(s) on the ascending aorta and/or aortic arch that do not require deep hypothermic arrest (deep
 

2.10	Exclusion Criteria:				
	Subjects will be required to meet none of the exclusion criteria:				
	
 
Admitted for surgical treatment of arrhythmia or Atrial fibrillation history;
 
				
	
 
Admitted for cardiac surgery requiring implantation/explantation of a Ventricular Assist Device (VAD) or heart transplant;
 
				
	3. Admitted for Transcatheter aortic valve replacement (TAVR);				
	
 
Cardiac surgical procedure that requires deep hypothermic arrest (as defined above);
 
				
	
 
New or active endocarditis or myocarditis that is not adequately controlled with medication and/or requires surgical intervention;
 
				
	

Documented inherited bleeding disorder(s);

				
	7. History or known allergies to the device materials; or				
	
 
Participation in another clinical investigation. If a subject has recently completed participation in another drug or device clinical investigation, the subject must have completed that study at least thirty (30) days prior to being enrolled in this clinical study.
 
				
2.11	Device:				
	ClearFlow's PleuraFlow ® Catheter System				
2.12	Indications for Use:				
	The PleuraFlow ® ACT ® System is indicated for use as an adjunctive device during open surgical procedures in order to prevent fluid accumulation within the operative site after closure of the surgical wound. The device is indicated for use in cardiothoracic surgical procedures.				
2.13	Endpoints:				
	2.13.1 Primary performance endpoint				
	
 
Rate of any episode of new onset of Post-Operative Atrial Fibrillation (POAF) in the study group. POAF is defined as any atrial fibrillation episode ≥ 60 min on telemetry or EKG. At any time between post index surgery through hospital discharge.
 
				

#### Rev. 4, Febuary 2016

- 2.13.2 Secondary performance endpoints
  - Rate of interventions to treat Retained Blood Syndrome (RBS). RBS is a composite endpoint defined as an intervention to treat one or more of the following conditions:

-Re-exploration for bleeding, tamponade or washout of retained blood [Time Frame: discharge from OR to 30 days post index surgery];

-Any procedure to treat Pericardial effusion; i.e., pericardial window, pericardiocentesis, placement of pericardial drain [Time Frame: discharge from OR to 30 days post index surgery];

-Any procedure to treat Pleural effusion; i.e., thoracentesis under any image-guided modality [Time Frame: discharge from OR to 30 days post index surgery];

-Any procedure to treat hemothorax (i.e., chest tube, thoracoscopy, thoracotomy, etc.) [Time Frame: discharge from OR to 30 days post index surgery]Any procedure to treat Pneumothorax. [Time Frame: discharge from OR to 30 days post index surgery].

- Readmission for any diagnosis of RBS and/or POAFrelated occurrences [Time Frame: within 30 days post index surgery].
- Readmission for any reason. [Time Frame: within 30 days post index surgery].

#### 2.13.3 Other Outcomes:

- Mortality [Time Frame: within 30 days post index surgery];
- Length of Hospital Stay [Time Frame: day of discharge];
- Stay in the Intensive Care Unit (ICU) [Time Frame: hours];
- Ventilation time [Time Frame: hours to extubation];
- Transfusion postoperative [Time Frame: total number and type of units used];
- Total chest tube output first 24 hours [Units: milliliters];
- Total chest tube drainage [Units: milliliters];

•	Any cardiac arrest [Time Frame: within 30 days post index surgery];
•	Stroke [Time Frame: within 30 days post index surgery];
•	Renal failure requiring dialysis [Time Frame: within 30 days post index surgery];
-	Renal insufficiency with serum creatinine level 3 times greater than baseline level or serum creat level $\geq$ 300 $\mu$ mol/L. [Time Frame: within 30 days post index surgery]; converter en umol/L pour nous.
•	Surgical Site Infection:
dui	-Sternal Superficial Wound Infection: (i) within 30 days st index surgery; (ii) 30 days post index surgery but ring hospitalization; (will be confirmed at postoperative rgeon appointment)
	-Deep Sternal Infection/Mediastinitis; within 30 days st index surgery (will be confirmed at postoperative geon appointment)
(wi	-Post-op Pneumonia; within 30 days post index surgery ill be confirmed at postoperative surgeon appointment)
	Septicemia [Time Frame: hospital discharge];
•	Sepsis [Time Frame: within 30 days post index surgery];
•	Urinary tract infection [Time Frame: within 30 days post index surgery];
Data	Management:
of Mo	will be collected and stored at the department of surgery ntreal Heart Institute. Only the princiapal investigator tudy coordinators will have access to the database.
Stat	istics
Samp	ole Size Calculations:
analy: the P	primary analysis will be an intention-to-treat (ITT) sis comparing the POAF rate in the PleuraFlow ® group to OAF rate in the control group. Based on findings from our utional clinical database at the Montreal Heart Institute,

the local incidence of POAF after cardiac surgery is approximately 25% (control group). The proportion in group Pleuraflow (the treatment group) is assumed to be 0,2500 under the null hypothesis and 0,1500 under the alternative hypothesis. Group sample sizes of 254 in each group achieve 80% power to detect a difference between the group

Rev. 4, Febuary 2016

2.14

2.15

proportions of 0,1000 using a Chi-Square test with a significance level of 0.0476. This significance level is computed using the O'Brien-Fleming method and accounts for the interim analysis that is planned after 300 randomized subjects have completed their 30-day follow-up.

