#### **Statistical Analysis**

POAF and intervention to treat RBS rates and all other categorical event rates will be compared using chi-square tests. Multiple logistic regressions to adjust for potential confounding factors will also be used. Odds ratio and associated 95% confidence intervals will be computed for descriptive purpose. Goodness of fit will be checked using Hosmer-Lemeshow statistics. Quantitative endpoints will be investigated using Student t-tests. Analysis of covariance may also be used to account for potential confounding factors. Nonparametric tests or data transformation may be used if normally quantitative endpoints are not distributed. Correlations and associated 95% confidence intervals will be computed for descriptive purpose.

An interim analysis will be conducted on the first 300 randomized subjects completing their 30-day follow-up. The primary endpoint (POAF rate) will be compared between the PleuraFlow® group and the control group using a chi-square test. The significance level for this test will be 0.0076, as computed using the O'Brien-Fleming method. If the p-value of the chi-square test is below this bound at the interim analysis, the study will be stopped for efficacy. Otherwise, the study will continue up to the planned 508 patients. As a result of this interim look, the final analysis of the primary endpoint would require a p < 0.0476 to be declared statistically significant. Analysis of the secondary endpoints and other outcomes will be conducted at the 0.05 significance level.

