#### 9.3 Exclusion Criteria

Subjects will be required to meet none of the Exclusion Criteria:

- 9.3.1 Admitted for surgical treatment of arrhythmia;
- 9.3.2 Admitted for cardiac surgery requiring implantation/explantation of a Ventricular Assist Device (VAD) or heart transplant;
- 9.3.3 Cardiac surgical procedure that requires deep hypothermic arrest (as defined above);
- 9.3.4 Admitted for Transcatheter aortic valve replacement (TAVR);
- 9.3.5 New or active endocarditis or myocarditis that is not adequately controlled with medication and/or requires surgical intervention;
- 9.3.6 Documented inherited bleeding disorders;
- 9.3.7 History or known allergies to the device materials; or
- 9.3.8 Participation in another clinical investigation. If a subject has recently completed participation in another drug or device clinical investigation, the subject must have completed that study at least thirty (30) days prior to being enrolled in this clinical study.

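### The renal insufficiency outcome scores any creatinine of 300 µmol/L or more within 30 days as an event, even when the patient was already at that level before surgery

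*Combined protocol and SAP*

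**What the plan says.** Section 2.13.3 (Other Outcomes) lists "Renal insufficiency with serum creatinine level 3 times greater than baseline level or serum creat level" and completes the second limb as "serum creat level $\geq$ 300 $\mu$ mol/L. [Time Frame: within 30 days post index surgery". The two limbs are joined by an or. Only the first refers to baseline. A leftover French working note about unit conversion follows the definition, which suggests that the wording was not finalised.

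The neighbouring item reads "Renal failure requiring dialysis [Time Frame: within 30 days post index surgery", with no statement about patients already on dialysis.

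On eligibility, section 9.3 says "Subjects will be required to meet none of the Exclusion Criteria". None of items 9.3.1 to 9.3.8 concerns creatinine, chronic renal failure or dialysis. The same is true of the inclusion criteria in 9.2 and of the synopsis exclusion list (2.10).

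On analysis, the Statistical Analysis section states "POAF and intervention to treat RBS rates and all other categorical event rates will be compared using chi-square tests", and sets 0.05 as the level for secondary and other outcomes. It adds "Multiple logistic regressions to adjust for potential confounding factors will also be used", without naming covariates. Odds ratios with 95% confidence intervals are to be given descriptively.

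**The concern.** A postoperative complication outcome should count something that happened after surgery. Under the second limb, a patient with a stable creatinine of 320 µmol/L before and after the operation is an event, although nothing changed. No eligibility criterion keeps such patients out, and no analysis rule sets them aside.

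The primary endpoint is protected against this problem. It is worded as "Rate of any episode of new onset of Post-Operative Atrial Fibrillation (POAF) in the study group", and section 9.2.3 bars a history of atrial fibrillation. The renal insufficiency outcome has neither safeguard.

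At stake is the reading of one complication rate. Events already present at baseline add about the same amount to both arms. They pull the ratio towards 1 and add noise to a rare outcome. If the intention was to count only new events, that rule is not written, and whether to apply it could be decided after the data are seen.

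**Working it through.** **The plan's own figure.** The only sample size in the documents is for the primary endpoint: 25% against 15%, significance level 0.0476, 80% power. The two-sided two-proportion formula with pooled variance and no continuity correction gives 254 per group, with power 80.04% at that size. It reproduces and does not depend on the renal definition.

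**Reading the rule.** A patient with baseline below 300 µmol/L must rise to be scored under either limb. A patient with baseline at or above 300 who stays there meets the second limb with no change. The defect is confined to this second group.

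**Size of the dilution.** The documents give neither the share of patients starting at or above 300 µmol/L nor a renal event rate, so these inputs are assumptions:
- b, prevalent cases scored as events in each arm: 1-2% of patients, or 508 × 0.01 = 5 to 508 × 0.02 = 10 patients in total.
- e, new events in the control arm: 2-3% of patients.
- A true halving of new events in the test arm.

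Scored rates are b + e (control) and b + 0.5e (test). The apparent risk ratio is (b + 0.5e)/(b + e).

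| b | e | Control | Test | Risk ratio | Odds ratio | Difference |
|---|---|---|---|---|---|---|
| 0 | 2% | 2.0% | 1.0% | 0.50 | 0.49 | 1.0 points |
| 0 | 3% | 3.0% | 1.5% | 0.50 | 0.49 | 1.5 points |
| 1% | 2% | 3.0% | 2.0% | 0.67 | 0.66 | 1.0 points |
| 1% | 3% | 4.0% | 2.5% | 0.63 | 0.62 | 1.5 points |
| 2% | 2% | 4.0% | 3.0% | 0.75 | 0.74 | 1.0 points |
| 2% | 3% | 5.0% | 3.5% | 0.70 | 0.69 | 1.5 points |

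The odds ratio, which is the plan's descriptive measure, is [t/(1 − t)]/[c/(1 − c)] for test rate t and control rate c. It moves with the risk ratio. The absolute difference is (b + e) − (b + 0.5e) = 0.5e, whatever b is.

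**A second set of assumptions.** Let new-event rates be 4% against 2% among patients not already at the threshold, with share q prevalent. Scored rates are q + (1 − q)p.
- q = 1%: 4.96% against 2.98%, risk ratio 0.60; prevalent cases are 0.01/0.0496 = 20% of control-arm events.
- q = 2%: 5.92% against 3.96%, risk ratio 0.67; prevalent cases are 0.02/0.0592 = 34% of control-arm events.

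Power at 254 per arm and 0.05 is 26% with no prevalent cases, 21% at q = 1% and 17% at q = 2%. Here the difference shrinks only by the factor 1 − q, from 2.00 to 1.98 or 1.96 points.

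**Type I error.** With no device effect, both arms have the same scored rate b + e. Exact enumeration of the chi-square test at 254 per arm, for b = 0-2% and e = 2-3%, gives rejection rates of 4.7-5.1%. Prevalent cases do not raise the false-positive rate.

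**The case against.** **Low power in any case.** Under the first set of assumptions, exact power to detect a halving is about 14% (e = 2%) or 20% (e = 3%) with no prevalent cases at all. It is about 9-11% or 13-16% with them. The outcome is one of many unpowered items and would support little inference even if perfectly defined. This stands, and it is why the point is minor. It does not make a definition correct that labels an unchanged value as a complication.

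**Analysts would count only new events.** The second study objective refers to complications after surgery, so a sensible reader might do this. For dialysis the argument has force: the item is listed with stroke and cardiac arrest, which also carry no qualifier, and is naturally read as a postoperative complication. For the creatinine limb it does not, because the written rule is explicit and says otherwise. The case report forms are in the Manual of Operations, which is not among the documents, so how baseline status is recorded is unknown.

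**Stronger readings a reader might infer.**
- That patients with advanced renal disease are automatic events in both renal outcomes from day 0. The two outcomes have different triggers. A patient at or above 300 µmol/L who is not on dialysis does not meet the dialysis item. A dialysis patient meets the creatinine limb only if a value within 30 days is at or above 300.
- That chance imbalance in prevalent cases could manufacture a significant result beyond the nominal rate. Imbalance is plausible: if 8 patients were prevalent cases, a split of 6:2 or worse has probability 2 × (28 + 8 + 1)/256 = 74/256, about 29%. But allocation is random 1:1 and the test already allows for this, as the type I error check shows.

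**Conclusion.** Wrong as written, and minor. The 300 µmol/L limb scores stable pre-existing renal failure as a postoperative event, and nothing in the eligibility or analysis sections prevents it. The consequence is dilution of the odds ratio and some loss of power for one of the other outcomes. Under 1:1 randomisation the misclassification is expected to be equal in both arms, so it should not favour either.

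The figures are illustrations. The risk ratio range of about 0.63-0.75 for a true halving rests on assumed shares of 1-2% prevalent cases and 2-3% new events, and on prevalent cases remaining at or above 300 on at least one postoperative measurement. Nothing here should be read as touching the primary or secondary endpoints, the interim rule or the sample size.

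**What to change.** Amend the definition in section 2.13.3 so that the 300 µmol/L limb counts only when preoperative creatinine was below 300 µmol/L. Analyse renal insufficiency in patients with baseline creatinine below 300 µmol/L who were not on dialysis before surgery, and report the number left out in each arm.

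The denominator restriction is needed as well as the change to the limb. Otherwise a non-dialysis patient with a baseline of 300 or more would stay in the analysis but could count only by tripling, to at least 3 × 300 = 900 µmol/L. An automatic event would become a near-automatic non-event.

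As a consistency point, define the dialysis outcome as new postoperative dialysis in patients not on dialysis before surgery.

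The cost is one or two sentences, with no change to sample size. Baseline creatinine is already needed for the tripling limb; preoperative dialysis status must be recorded if it is not already. The denominator becomes slightly smaller, and worsening in patients with advanced renal disease at baseline is no longer assessed by this outcome.

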#### **Statistical Analysis**

POAF and intervention to treat RBS rates and all other categorical event rates will be compared using chi-square tests. Multiple logistic regressions to adjust for potential confounding factors will also be used. Odds ratio and associated 95% confidence intervals will be computed for descriptive purpose. Goodness of fit will be checked using Hosmer-Lemeshow statistics. Quantitative endpoints will be investigated using Student t-tests. Analysis of covariance may also be used to account for potential confounding factors. Nonparametric tests or data transformation may be used if normally quantitative endpoints are not distributed. Correlations and associated 95% confidence intervals will be computed for descriptive purpose.

An interim analysis will be conducted on the first 300 randomized subjects completing their 30-day follow-up. The primary endpoint (POAF rate) will be compared between the PleuraFlow® group and the control group using a chi-square test. The significance level for this test will be 0.0076, as computed using the O'Brien-Fleming method. If the p-value of the chi-square test is below this bound at the interim analysis, the study will be stopped for efficacy. Otherwise, the study will continue up to the planned 508 patients. As a result of this interim look, the final analysis of the primary endpoint would require a p < 0.0476 to be declared statistically significant. Analysis of the secondary endpoints and other outcomes will be conducted at the 0.05 significance level.

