# 9 Study Population

### 9.1 Demographics

-Up to 508 evaluable post-cardiac surgery female and male subjects, 18 years of age and older will be consecutively enrolled in the study.

- Subjects are required to meet all inclusion criteria and none of the exclusion criteria to be included in this PMCF study. Subjects must be informed about this study and a written and signed informed consent must be obtained from the subject prior to cardiac surgery.

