#### **10.5 Randomization**

Subjects who meet eligibility criteria will be randomly assigned in a 1:1 fashion to either the Test arm or the Control arm.

The point of randomization is before the start of the index surgery. Subject assignment will be provided to the operating surgeon at that time.

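### The decision test for postoperative atrial fibrillation leaves age and planned surgery type unused; a prespecified adjusted test is a cheap, modest and uncertain improvement, not the repair of an error

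*Combined protocol and SAP*

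**What the plan says.** The Statistical Analysis text of the synopsis says "POAF and intervention to treat RBS rates and all other categorical event rates will be compared using chi-square tests". The sample size rests on the same test, "using a Chi-Square test with a significance level of 0.0476". At the interim look, after 300 patients have completed 30 days, the chi-square is judged at 0.0076, and its p-value alone can end the trial: "If the p-value of the chi-square test is below this bound at the interim analysis, the study will be stopped for efficacy".

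Logistic regression is planned in addition, to adjust for possible confounders. The covariates are not named, and the resulting estimates have no part in the decision: "Odds ratio and associated 95% confidence intervals will be computed for descriptive purpose".

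Section 10.5 fixes the timing: "The point of randomization is before the start of the index surgery". Three factors are therefore known by then:

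- **Age.** It is checked for eligibility (section 9.1: "18 years of age and older will be consecutively enrolled in the study").
- **Planned surgery.** The inclusion criteria in the synopsis and section 9.2 list "Admission for CABG, valve replacement or valve repair surgery, or a combination of these surgeries" and certain aortic procedures.
- **Hospital, if there are two.** The synopsis gives "Up to 508 evaluable subjects enrolled at the Montreal Heart Institute and Sacré-Coeur of Montreal Hospital", while the synopsis and section 8 also call the study single-centre.

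Allocation is 1:1, and no stratification factor is named.

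**The concern.** When baseline factors predict a binary outcome, a test that adjusts for them usually has somewhat more power than the crude comparison and gives a narrower interval for the risk difference, at no cost in patients. This trial would hold those values for every patient and does not use them in the test that can stop it or declare success. The planned power is 80% with no margin, and the documents state no allowance for dropout.

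There is a second, smaller matter. Because the covariates of the additional logistic models are unnamed, the adjusted result could depend on choices made after the data are seen. What is at stake is a modest amount of power and precision, not the validity of the primary conclusion.

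**Working it through.** **Inputs from the documents.** POAF 25% in control and 15% with the device; 254 per arm; levels 0.0076 at 300 patients and 0.0476 at 508; 1:1 allocation. Sidedness is not stated. Only a two-sided test reproduces 254 (a one-sided test needs 201).

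**Step 1: reproduce the plan.** Chi-square with pooled variance and no continuity correction, mean rate 0.20:

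power = Φ[(0.10 − z·√(2·0.20·0.80/n)) / √((0.25·0.75 + 0.15·0.85)/n)]

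- Final, n = 254, z = 1.981: (0.10 − 1.981 × 0.03549)/0.03522 = 0.843, so power is 80.04%. The plan's figure is confirmed.
- Interim, n = 150, z = 2.669: (0.10 − 2.669 × 0.04619)/0.04583 = −0.508, so power is 30.6%.

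**Step 2: rough size of a gain.** If the covariates explain a share R² of the outcome variance, the effective size is about 254/(1 − R²) per arm. Putting this in the formula gives:

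| R² | 0 | 0.01 | 0.02 | 0.05 | 0.10 |
|---|---|---|---|---|---|
| Power | 80.0% | 80.4% | 80.8% | 82.0% | 84.1% |

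The documents give no R², no POAF rate by age, surgery or hospital, and no case mix. Everything from here on rests on assumptions.

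**Step 3: simulation.** 20,000 trials per setting, 508 patients, unstratified 1:1, marginal rates held at 25% and 15%. Assumed: surgery mix 60/30/10% (CABG / valve / aortic) and 30% of patients at a second hospital. Assumed odds ratios for hospital / valve and aortic / age per SD: mild 1.2/1.3/1.25, moderate 1.3/1.6/1.5, strong 1.5/2/2. The adjusted test is the Wald test of treatment in a logistic model with all three factors.

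| | Mild | Moderate | Strong |
|---|---|---|---|
| Control-arm AUC | 0.58 | 0.63 | 0.70 |
| Final power, chi-square | 80.4% | 80.4% | 80.4% |
| Final power, adjusted | 80.7% | 81.3% | 83.4% |
| Paired change, points | +0.2 | +0.9 | +3.0 |
| Interim power, chi-square | 30.0% | 29.8% | 29.6% |
| Interim power, adjusted | 29.5% | 30.0% | 32.4% |
| Risk-difference interval narrower by | 0.4% | 1.6% | 4.5% |

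The paired standard error is 0.1 to 0.2 points, so the mild gain cannot be told from zero. Inverting the Step 1 formula, the three gains are worth about 3, 12 and 41 patients.

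**Step 4: how firm is the range?** A rerun of the same settings with 6,000 trials each gave −0.1, +1.2 and +3.1 points. Separate runs with other assumed mixes and odds ratios (6,000 trials each) gave 81.2% against 80.6% adjusted when nothing was prognostic (−0.6), and 79.8% against 83.7% at R² 0.104 (+3.9). The range is therefore about −0.5 to +3 points for weak to strong prognosis, and about +4 beyond that.

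**Step 5: which factor matters?** With the odds ratios of Step 3, age alone gives +0.1/+0.6/+2.2 points and hospital with surgery −0.1/+0.1/+0.3. With surgery made dominant instead (valve 2.5, aortic 3, age 1.25 per SD, hospital 1.3), power was 80.0% unadjusted, 80.1% with age, 81.2% with surgery and 81.6% with all three. The ranking follows the assumptions.

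**Step 6: type I error.** Null rejection over both looks for the adjusted Wald test was 0.0498/0.0508/0.0528, against 0.0498/0.0498/0.0512 for the chi-square. The strong-case paired difference is +0.0016 (SE 0.0012), so there is no material change. A test on the standardised risk difference itself rejected slightly too often at the interim look: 0.0091/0.0083/0.0094 against 0.0076.

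**The case against.** The strongest reply is that the plan contains no defect. The test, the two levels and the sample size agree with one another; the chi-square is legitimate under 1:1 randomisation and addresses directly the 25% against 15% contrast the trial was sized on; and adjusted logistic models are already planned. On that view, naming their covariates is enough. With weak covariates the proposed test gains nothing and may lose about half a point, and deciding on a conditional log odds ratio while reporting a marginal risk difference brings in two procedures that can disagree near the boundary.

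Most of this stands. It limits the point to an optional improvement, and the downsides are real. It does not remove the point: the existing models cannot affect the decision, and the baseline values are already held.

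Several stronger readings are tempting, and the documents support none of them:

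- **That the chi-square is wrong or underpowered.** Step 1 reproduces its stated power.
- **That age would supply most of the gain.** The documents give age only as an eligibility limit, and Step 5 shows the ranking reverse under other assumptions.
- **That a gain is assured.** It may be zero or slightly negative.
- **That hospital should go straight into the model.** The documents disagree on whether there is one site or two. That conflict is editorial and is no argument for adjustment.

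**Conclusion.** The point holds as a low-cost improvement. The only decision test at either look is unadjusted, although age and planned surgery type (and hospital, if two sites take part) are fixed before randomisation. Adjusting for them would change final power by about −0.5 to +3 points, or about +4 with prognosis stronger than the strong case assumed here, without a material change in type I error. These figures rest wholly on assumed odds ratios, surgery mix and hospital share. The documents do not show where in the range this trial lies or which covariate matters. A reader might infer that the trial could enrol fewer patients; a gain this small and uncertain does not support that.

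**What to change.** Before the 300-patient look, amend the analysis text as follows.

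1. Make the primary test the Wald test of the treatment term in a logistic model with treatment, age (linear) and planned type of surgery (isolated CABG; valve with or without CABG; any aortic procedure), at the existing levels 0.0076 and 0.0476.
2. Add hospital only once the two named hospitals and the single-centre label have been reconciled.
3. Fix in advance a rule for merging a sparse aortic group with the valve group, applied blind to arm.
4. Report the standardised risk difference with its confidence interval as the effect estimate. Take the decision from the treatment term, given the interim over-rejection in Step 6.
5. Keep the chi-square as a supportive analysis and leave the sample size at 508.

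It is sensible first to estimate how well these factors predict POAF in the institutional database cited in section 4. If the AUC is near 0.58, the gain is about nil and the chi-square can reasonably stay primary, with the covariates of the additional models named.

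**Cost.** The change is to analysis wording and programming; it needs no added patients, no new data and no new randomisation list. The price is a conditional odds ratio that needs the risk difference beside it, possible disagreement between the test and that interval near the boundary, and about half a point of power if the covariates turn out weak.
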